9.5 Statistical Analysis for Correlative Studies

We expect that at least 60-70% of samples collected for correlative studies will be adequate for analysis. The statistical plan for the first and the third aim is based on the assumption of 132 patients (62% samples of 212 patients randomized before May 19, 2010 and after September 24) are available for analysis of correlative studies. The statistical plan for the second aim is based on the assumption of 16 del5q31.1 patients (62% samples of 26 del5q31.1 patients enrolled to the study) are available for analysis of correlative studies.

- 9.5.1 Evaluate the effect of CD45 isoform profile on lenalidomide enhancement of erythropoietin-induced STAT5 phosphorylation in CD71^{Hi} erythroid precursors and the relationship to erythroid response.

The association between the CD45 isoform profile and ex vivo augmentation of STAT5 phosphorylation by lenalidomide will be assessed by simple regressions. The phosphorylation delta (PD) as quantified by the log₁₀ ratio of p-STAT5 geometric mean fluorescence intensity (MFI) with lenalidomide (LEN)+ erythropoietin versus erythropoietin treatment alone (i.e., LEN+erythropoietin:EPO) will be regressed on RA:RO, RB:RO ratios separately. With 132 non-del5q31.1 patients, there is 83% and 94% power to test this association at a two-sided significance level of 0.05, if the true but unknown correlation between PD and RA:RO (or RB:RO) ratio is 0.25 and 0.3 respectively. The relationship between the CD45 isoform profile and MER response status will be assessed by treatment arm. RA:RO and RB:RO ratios will be compared between MER responders and non-responders within each treatment arm using the Wilcoxon rank sum test. The same assessment will be performed on the relation between PD and MER response status, and on the relation between apoptosis reduction and MER response status.

Prior studies show that response rate to erythropoietin varies for patients with different serum erythropoietin levels. To investigate if the addition of DA benefits the group of patients with sub-optimal erythropoietin production at baseline, MER response rates will be compared between treatment arms in the subset of patients with low serum erythropoietin levels at baseline (defined as <500 mU/ml) using Fisher's exact test. Furthermore, to investigate if primary resistance to lenalidomide monotherapy is due to low endogenous erythropoietin production, the change in serum erythropoietin levels at 16 weeks

from baseline of non- del5q31.1 patients on the monotherapy arm will be compared between MER responders and non-responders using Wilcoxon rank sum test. It is hypothesized that the decline in serum erythropoietin levels correlates with non-response.

The correlation between the magnitude of erythropoietin/STAT5-PD induced ex vivo by lenalidomide in pretreatment specimens and the magnitude of in vivo activation will be assessed using simple regressions by treatment arms. With 66 non- del5q31.1 patients per arm, there is 84% and 93% power to test this association at a two-sided significance level of 0.05, if the true but unknown correlation between PD and RA:RO (or RB:RO) ratio is 0.35 and 0.4 respectively.

Characterize molecular targets relevant to lenalidomide cytotoxicity in del5q31.1 cells

To determine whether lenalidomide modulates the phosphatase activity of Cdc25C and PP2A in bone marrow MNC from MDS patients with or without del5q31.1, a series of comparisons will be made. The RNA and protein expression level of Cdc25C, PP2A and their phosphatase substrates, Cdc2phospho-Tyr15 and Cdc25Cphospho-Ser216 will be compared between 16 MDS patients with del5q31.1, 20 MDS patients with normal cytogenetics that are not receiving active therapy and 20 age-matched normal volunteers. Pair-wise comparisons will be conducted by using t-test. Under the assumption of equal variances of groups, with the above number of samples per group, the t-test has at least 82% power to detect an effect size of 1 standard deviation for each pair-wise comparison at a two-sided significance level of 0.05.

In the factorial experiment for the investigation of whether reduction of either Cdc25C or PP2A alone or in combination leads to lenalidomide sensitization in patients with normal karyotype, each patient's sample will be aliquotted to 4 equal portions which are randomly exposed to 4 conditions, the cross of inhibition or not inhibition of gene expression of Cdc25C and PP2A by siRNAs. This experiment will be performed in samples from twenty patients. Assume that 50% of MDS cases enrolled to the E2905 trial will have normal cytogenetics by conventional metaphase karyotyping and that 5% of MDS cases with normal cytogenetics may contain minor abnormalities in the 5q31.1 CDR by SNA arrays, to arrive at 20 patients with normal karyotype, 45 bone marrow samples (each from an individual MDS patient) eligible for analysis need to be obtained. Apoptosis and cell cycle from this randomized blocks design will be analyzed by using Analysis of Variance (ANOVA) with the blocking variable patient as the random effect.

- 9.5.2 Evaluate the frequency of cryptic chromosome 5q31.1 deletions in patients with non- del5q31.1 MDS by array-based genomic scan, and to determine the relationship to hematologic response

Signal intensity will be analyzed and SNP calls determined using Gene Chip Genotyping Analysis Software Version 4.0 (GTYPE). Copy number will be investigated using a Hidden Markov Model and Copy

Number Analyzer for Affymetrix GeneChip Mapping 1000K arrays (CNAG v.3.0)22. Segmental LOH will be identified by a statistical assessment of the likelihood that consecutive SNP loci would exhibit heterozygosity given the corresponding allelic frequency of particular SNP in the normal population (CNAG). Lesions identified by SNP arrays will be compared with the Cancer Genome Anatomy Project database (<http://cgap.nci.nih.gov>). The two-sided Fisher's Exact test will be used to analyze the difference between the distributions of dichotomized variables among the groups. Normal copy number polymorphisms will be identified according to <http://projects.tcag.ca/variation/>.

LOH that correlates with response/refractoriness will be identified through the following approach. Frequencies of LOH within q-arm of chromosome 5 will be compared between hematologic responders and non-responders using Fisher's exact test. To control for false positives, nominal p-values from Fisher's exact tests will be adjusted such that the FDR (false positive rate) is controlled under 5%. Distribution of cryptic copy number changes of SNP on the q-arm of chromosome 5 will also be compared between hematologic responders and non-responders using the Chi-square test. False positives will also be controlled as in the LOH analysis. Analogous calculations are planned for the exploration of presence of "any lesion" throughout the genome, numbers of lesions and each specific lesion type (e.g. 7q, UPD7q etc) and its association with response/non-response.

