11.2.3.2 To characterize molecular targets relevant to lenalidomide cytotoxicity in del5q

We have shown that LEN inhibits the PPT activity of both Cdc25C and PP2A *in vitro*. We hypothesize that enforced reduction in Cdc25C expression, using siRNA, mimics the naturally occurring events of haplo-deficiency in del5q AML and MDS cells. The goal of this specific aim, using U937-siCdc25c cells as a model, is to determine whether inhibition of Cdc25C mediates the cellular apoptotic events associated with LEN treatment. We will further define whether Cdc25C and PP2A coordinately regulate cell survival in U937 cells. Finally, we will utilize a siRNA retroviral-based expression system targeting Cdc25C and PP2A to determine whether coordinated disruption of these two PPTs induce apoptosis in cells from non-del5q MDS patients *in vitro*. Through experiments proposed in this specific aim, we will provide important biochemical and molecular information about LEN mechanisms of action. Understanding the signaling mechanisms of LEN will better enable the development of targeted drug therapy for MDS; selecting inhibitors for key signaling events that mediate survival and transformation of the leukemic clones.

11.2.3.3 To evaluate the frequency of cryptic chromosome 5q31 deletions in patients with non-del5q MDS by array-based genomic scan, and to determine the relationship to hematologic response.

The main goal of the proposed studies is to delineate sub-microscopic chromosome 5q31 deletions that are not resolved by conventional metaphase cytogenetics. For that purpose, high-density array-based genome mapping will be performed to characterize molecular markers for response and identify cryptic chromosomal lesions that

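### The analysis meant to show whether lenalidomide modulates Cdc25C and PP2A compares patient groups, not drug exposure, so none of its results can be attributed to lenalidomide

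*Combined protocol and SAP*

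**What the plan says.** The text is in the unnumbered part of Section 9.5 on molecular targets in del5q31.1 cells, between 9.5.1 and 9.5.2. It serves objectives 2.2.5 and 2.2.8.3.

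- **Aim:** "To determine whether lenalidomide modulates the phosphatase activity of Cdc25C and PP2A in bone marrow MNC from MDS patients with or without del5q31.1".
- **Measurements:** "The RNA and protein expression level of Cdc25C, PP2A and their phosphatase substrates, Cdc2phospho-Tyr15 and Cdc25Cphospho-Ser216 will be compared".
- **Groups:** "16 MDS patients with del5q31.1, 20 MDS patients with normal cytogenetics that are not receiving active therapy and 20 age-matched normal volunteers".
- **Test:** "Pair-wise comparisons will be conducted by using t-test".
- **Power:** equal variances are assumed, and "the t-test has at least 82% power to detect an effect size of 1 standard deviation". Each pair of groups is tested two-sided at 0.05.

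The sampling time of the del5q group is not stated. Section 4.3.3 assigns every del5q31.1 patient to lenalidomide monotherapy, so the trial has no untreated del5q group. Section 11.2.3.2 says that lowering Cdc25C by siRNA "mimics the naturally occurring events of haplo-deficiency in del5q AML and MDS cells".

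**The concern.** The question concerns a drug effect and the analysis concerns group membership. A test of whether lenalidomide modulates a target needs the same kind of cells with and without lenalidomide. The plan instead sets a karyotype-defined patient group against a different patient group and against healthy people, so the contrasts differ by karyotype, by disease status, or by both.

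The protocol itself gives a reason to expect a difference between del5q and non-del5q cells without any drug, at least for Cdc25C. A significant t-test placed under an aim about lenalidomide modulation could then be read as evidence of drug action. At stake is how the laboratory evidence on mechanism in del5q disease is interpreted. The primary endpoint is not touched.

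**Working it through.** **1. The plan's own figures.** The expected number of del5q patients is 252 − 226 = 26, and 62% of 26 is 16.1, hence 16. For a two-sample t-test with equal variances, power comes from the noncentral t distribution with noncentrality d × √(n₁n₂/(n₁+n₂)) and n₁+n₂−2 degrees of freedom, at two-sided 0.05.

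- 16 vs 20, d = 1: noncentrality √(320/36) = 2.98, 34 df, power 82.5%.
- 20 vs 20, d = 1: noncentrality √(400/40) = 3.16, 38 df, power 86.9%.

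The smaller value reproduces the stated 82%. The arithmetic is right, but it is power for a difference between groups.

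**2. What the comparison can identify.** The unstated time point leaves two cases.

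- *All samples pre-treatment:* nobody has been exposed, so no lenalidomide effect can be estimated.
- *Del5q samples on treatment:* the MDS comparator is off active therapy, so exposure and karyotype coincide and cannot be separated.

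In neither case can a result be attributed to the drug.

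**3. Whether another part of the plan supplies the contrast.**

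- The siRNA factorial in Section 9.5 crosses Cdc25C inhibition (yes/no) with PP2A inhibition (yes/no) in normal-karyotype samples. Lenalidomide is not a crossed factor, and the outcomes are apoptosis and cell cycle.
- Section 11.2.3.2 cites in vitro inhibition already shown and plans U937 and siRNA work. It specifies no comparison of patient marrow with and without lenalidomide.
- The STAT5 aim (Sections 9.5.1 and 11.2.3.1) does have such contrasts: ex vivo with and without lenalidomide, and pre-treatment versus week 16. Neither is written for Cdc25C or PP2A.

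The aim also names phosphatase activity, whereas the listed measurements are expression and phospho-substrate levels. Activity is therefore addressed indirectly at best.

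**4. Chance of a significant test with no drug effect.** The documents give no size for the gene-dose difference, so it is varied. Del5q versus normal-cytogenetics MDS, 16 vs 20:

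| Assumed gene-dose difference | Noncentrality | Probability of p < 0.05 |
|---|---|---|
| 0.5 SD | 1.49 | 30% |
| 1.0 SD | 2.98 | 83% |
| 1.5 SD | 4.47 | 99% |

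**5. What a within-patient contrast would give.** For a shift of 1 between-patient SD and within-patient correlation ρ, the SD of the paired difference is √(2(1−ρ)). The paired t-test then has noncentrality √n/√(2(1−ρ)) with n−1 df. The documents do not give ρ, so it too is varied. With n = 16, the standardised paired difference detectable at 80% power is 0.749, which multiplied by √(2(1−ρ)) gives the last column.

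| ρ | Noncentrality, n = 16 | Power, 16 del5q pairs | Power, 20 normal-karyotype pairs | Shift detectable at 80% power, n = 16 |
|---|---|---|---|---|
| 0 | 2.83 | 75% | 85% | 1.06 SD |
| 0.3 | 3.38 | 88% | 95% | 0.89 SD |
| 0.5 | 4.00 | 96% | 99% | 0.75 SD |
| 0.7 | 5.16 | 99.8% | >99.9% | 0.58 SD |

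Comparing the paired changes between karyotypes (16 vs 20, difference in changes of 1 SD) has power 54%, 69%, 83% and 96% at the same four correlations.

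**The case against.** The best defence is that this is under-specification and not a design fault. Section 9.5 announces a series of comparisons. The neighbouring experiment is about sensitization to lenalidomide yet lists only siRNA conditions, so the section evidently does not record every bench condition; an ex vivo drug step may simply be unwritten. Other planned work also serves the objectives, and expression by karyotype is a legitimate contribution to characterising targets in del5q cells. The work is an optional, consent-dependent correlate in patients whom Section 9 leaves out of the comparative analysis.

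Part of this stands. The other work means that objectives 2.2.5 and 2.2.8.3 do not rest on this comparison alone, though a reader might infer that they do. An unwritten exposure step cannot be ruled out. It is also too strong to say that lenalidomide is certainly absent from every contrast, because the time point is open and on-treatment del5q samples would put drug on one side.

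What does not stand is the conclusion that only detail is missing. The groups, test and power are all written out, and under either reading of the timing they cannot answer the stated question.

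**Conclusion.** The point holds as a mismatch between aim and contrast. The stated power of at least 82% is correct, but only for a difference between groups defined by karyotype and disease status; no outcome of these t-tests supports a statement about lenalidomide.

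Three limits apply.

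- A reader might infer that gene-dose loss would be reported as a drug effect. The plan gives no interpretation rule, and its authors already treat Cdc25C haplo-deficiency as a feature of del5q cells. The text supports only that a difference could be read that way.
- Haplo-deficiency is documented for Cdc25C. The gene-dose argument should not be extended to PP2A on these documents.
- The 30%, 83% and 99% rest on assumed differences of 0.5, 1.0 and 1.5 SD. The 75% to 99.8% for paired testing rest on an assumed correlation of 0 to 0.7.

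This is a correlative aim. The MER comparison and its error rates are unaffected.

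**What to change.** **Minimum change, wording only.** State that the del5q and comparator samples are baseline samples. Relabel the three-group test as baseline expression by karyotype and disease status. Say that no conclusion about lenalidomide modulation will be drawn from it and that the 82% power refers to that group difference. This costs nothing.

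**To keep the lenalidomide aim.** Make its test a paired within-patient contrast, analysed separately in del5q and normal-karyotype patients:

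- *Preferred where cell yield allows:* the same baseline marrow ex vivo with and without lenalidomide.
- *Otherwise:* baseline versus week 16, from marrow already requested under Section 11.2. State the caveat that loss of the del5q clone (70% cytogenetic response in MDS-003, Section 1.2) changes the cells being measured. In normal-karyotype patients, week-16 pairs isolate lenalidomide only on Arm A, because Arm B also receives epoetin alfa. The plan does not say whether the 20 off-therapy patients are trial participants, so this should be stated too.

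The ex vivo option costs extra cells and assay work. The existing ex vivo step is flow cytometry on CD71-high precursors, aimed at non-del5q disease, whereas this aim needs RNA, protein and phospho-substrate assays on mononuclear cells. Both would draw on a 5 mL aspirate shared with the other studies, so the documents do not support treating it as one spare aliquot. If yield does not allow it and week 16 is judged unsuitable, the minimum change is enough.

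### Section 9.5.2 tests 5q copy-number changes with an unspecified Chi-square test on likely sparse tables, although the same section uses Fisher's exact test for LOH and for dichotomized variables

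*Combined protocol and SAP*

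**What the plan says.** Section 9.5.2 covers the array-based search for cryptic 5q31.1 deletions and their relation to response, which serves objective 2.2.8.4. It names tests in three places:

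- In general: "The two-sided Fisher's Exact test will be used to analyze the difference between the distributions of dichotomized variables among the groups".
- For LOH: "Frequencies of LOH within q-arm of chromosome 5 will be compared between hematologic responders and non-responders using Fisher's exact test". The nominal p-values are then "adjusted such that the FDR (false positive rate) is controlled under 5" percent.
- For copy number, the distribution of changes on the q-arm "will also be compared between hematologic responders and non-responders using the Chi-square test". The multiplicity step is the same: "False positives will also be controlled as in the LOH analysis".

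The section then plans analogous calculations across the genome for any lesion, the number of lesions and specific lesion types, without saying which of the two tests carries forward. No continuity-corrected, exact or permutation version of the Chi-square test is named. Nor does 9.5.2 say whether the arms are pooled.

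The opening of section 9.5 bases the first and third aims on "132 patients (62% samples of 212 patients randomized before May 19, 2010 and after September 24"). The only carrier frequency in the documents is in the text on the siRNA experiment: "5% of MDS cases with normal cytogenetics may contain minor abnormalities in the 5q31.1 CDR by SNA arrays". There it is used to count the samples that experiment needs.

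**The concern.** A cryptic lesion is by nature rare, so a table of lesion by response will have small counts among carriers. The Chi-square reference distribution is unreliable there, and its p-value depends on whether the software applies a continuity correction. Because the p-values feed an FDR step over many loci, what matters is their accuracy in the far tail, where the approximation is weakest. At stake is which lesions are reported as linked to response, and whether the 5% error rate attached to that list is right. The section already uses an exact test for tables of the same kind from the same arrays and patients, and gives no reason for the difference.

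**Working it through.** **Inputs**

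- Samples: 132 (section 9.5). Check: 0.62 × 212 = 131.4, and 132/212 = 62.3%, so the plan's figure reproduces.
- Response: 30% in Arm A and at least 50% in Arm B (section 9.2). Equal arms give (30% + 50%)/2 = 40% pooled, or 53 responders and 79 non-responders. Reading hematologic responder as MER is an assumption.
- Lower response: section 9.2 cites 25%-34% on lenalidomide alone. At 30%, 132 splits 40/92; at 27%, 36/96; at 25%, 33/99.
- Carrier rate: 5%, borrowed from normal-cytogenetics cases at the 5q31.1 CDR. Section 9.5 assumes that 50% of cases have normal cytogenetics.

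**Expected carrier cells at 40% response**

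- 5% of all 132 = 6.6 carriers: 6.6 × 0.40 = 2.6 responders, 6.6 × 0.60 = 4.0 non-responders.
- 5% of the 66 normal-cytogenetics samples = 3.3 carriers: 1.3 and 2.0.
- Both cells reach 5 only with 13 carriers (13 × 0.40 = 5.2; 12 × 0.40 = 4.8), about 10% of 132.

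**Pearson against Fisher**

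Let K carriers all be responders, with R responders, N non-responders and n = R + N. Then uncorrected Pearson X² = nKN / [R(n − K)], and the Fisher tail is C(R,K)/C(n,K). In these examples the opposite extreme table is more probable, so the two-sided Fisher p equals that tail.

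- 53/79, 3 carriers: X² = 132·3·79/(53·129) = 4.58, p = 0.032. Fisher = (53·52·51)/(132·131·130) = 0.063. Ratio 1.9.
- 40/92, 3 carriers: Pearson 0.0079, Fisher 0.026. Ratio 3.3.
- 40/92, 6 carriers: X² = 132·6·92/(40·126) = 14.46, p = 0.00014. Fisher 0.00059. Ratio 4.1.

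Over all tables with 3 to 8 carriers and Pearson p < 0.05, the ratio at 53/79 is about 1.3 to 2.0. The largest is 6 carriers, none responding: 0.040 against 0.081. At 40/92 with all carriers responding it runs from 3.3 to 4.4. For Arm A alone at 30% (20/46) it runs from 3.5 to 4.6.

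**Size of a single test**

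Given the number of carriers, the true size of the nominal 0.05 Pearson test at 53/79 moves from 0.009 (5 carriers) to 0.081 (6 carriers). Averaged over a 5% carrier rate it is 0.046 at nominal 0.05 and 0.0047 at nominal 0.01, so not inflated.

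**FDR under a global null**

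Benjamini-Hochberg at 5% (the plan names no procedure), independent loci, 2×2 tables, 132 samples, 5,000 runs per setting. Ranges are over the settings listed.

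| Responders | Carriers | Loci | Pearson | Fisher |
|---|---|---|---|---|
| 40% (53/79) | 5%, 10% | 10-1,000 | up to 0.042 | up to 0.031 |
| 30% (40/92) | 5-10% | 100-2,000 | 0.027-0.071 | up to 0.025 |
| 27% (36/96) | 5-10% | 100-2,000 | 0.047-0.125 | up to 0.025 |
| 25% (33/99) | 5-10% | 100-2,000 | 0.068-0.136 | up to 0.029 |

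Where Pearson exceeds 5% the value is typically 0.06 to 0.12. At 30% responders with 5% carriers it stays close to or below 5%.

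**The case against.** Four objections have weight.

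1. **The harm does not appear under the plan's own response rates.** A reader might infer that the FDR control is broken as planned. At 40% pooled response it is not: the simulated FDR stays below 5%. It also stays below 5% for Arm A alone (20/46, 66 samples, 2.5-5% carriers), at 0.022 or less. The excess needs 132 samples with only 25-30% responders, that is, a combination arm doing little better than monotherapy.
2. **A larger Fisher p-value is not proof that Pearson's is too small.** Fisher's test is conservative with few carriers, and part of the ratio reflects that. A reader might take about 4 times as the general understatement. It applies near 30% responders with every carrier responding; at the pooled rate the figure is about 2.
3. **The documents do not say that 5% of patients carry a 5q copy-number change.** That rate is for normal-cytogenetics cases and one region, while the test covers the whole q-arm in all non-del5q31.1 patients. The sparse-cell figures therefore rest on an assumption.
4. **The version of the test is open, and the text may not mean a 2×2 table.** With Yates' correction the direction mostly reverses (6 of 6 carriers responding at 53/79: 0.0084 against Fisher's 0.0035). The copy-number sentence can mean loss/normal/gain, and the general sentence on dichotomized variables may already send two-category tables to Fisher.

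The first three limit the size of the problem. The fourth shows that the plan leaves the p-value undetermined, which supports naming the test.

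**Conclusion.** The point holds as a minor one. Section 9.5.2 prescribes an unspecified Chi-square test next to Fisher's exact test for closely similar tables, and the mismatch needs no assumption to see. On the borrowed 5% rate, expected carrier cells are about 1.3 to 4.0. Uncorrected Pearson p-values are up to about 2 times below Fisher's at the planned pooled response, and about 3 to 4.5 times below at 30% responders when all carriers respond. FDR control holds at the planned rates and can fail at a 25-30% responder share with many loci, where Fisher's stays at or below about 0.03. These figures assume uncorrected Pearson, two-category tables, Benjamini-Hochberg and independent loci; neighbouring SNPs are correlated, so the simulated rates are indicative only. The analysis is exploratory and has no bearing on the primary endpoint, the sample size or the stopping boundaries.

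**What to change.** In section 9.5.2, replace the Chi-square test for the 5q copy-number comparison with the two-sided Fisher's exact test, or with its Fisher-Freeman-Halton extension if loss, normal and gain are kept as three categories. State that the same tests apply to the categorical genome-wide comparisons before the FDR adjustment. In the same edit, say whether the arms are pooled.

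This costs a sentence or two and needs no new data. The downside is somewhat larger p-values for rare lesions, hence some loss of power to flag them.
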